
Sample Size Statistical Rationale
	
Primary Efficacy Endpoint (at 6 months post- implant):
 
The primary endpoint will be the 6 month incidence of HF related Hospitalizations or all-cause mortality, compared to a performance goal (PG).
 
The statistical PG of 0.43 is derived from published results from clinically relevant, contemporary studies of NYHA class III HF subjects.
 
For study success, the upper confidence bound of the observed event rate for the planned study must be less than the PG₆. Additionally, we require the observed event rate to be less than 0.37.
 
Evaluating the upper bound of the confidence interval for the rate, ensures that 1) the observed rate will be comparable to prior studies of active treatment (highest observed value = 0.44), 2) the observed rate will be less than the mean rate from meta- analysis of prior studies of treatment and control, and 3) the observed rate will be less than the lowest rate observed in the control studies (GUIDE-HF). The added requirement for the observed rate to be less than 0.37 provides further assurance that results are comparable to studies of prior treatment.
 
Based on this, the study will implant 450 subjects (single arm cohorts) leading to an expected evaluable cohort of 406 subjects. With a PG of 0.43 and a one-sided 0.025 alpha level, the study will have greater than 80% power assuming a population treatment rate of 0.34. Calculations are based on a one-sample Poisson rate test and were performed with PASS 2021.
 
Primary Safety Endpoints
 
There are two primary safety endpoints.
 
Freedom from device or system related complications at 6 months will be tested against the null rate of 90%. Based on a one sample test of a proportion, a sample size of 450 patients provides greater than 95% power assuming a population rate of 95% based on a two-sided Type I error rate of 5%.
 
Similarly, Freedom from Pressure Sensor Failure at 6 months will be tested against the null rate of 95%. Based on a one sample test of a

	proportion, a sample size of 450 patients provides greater than 95% power assuming a population rate of approximately 98.4% based on a two-sided Type I error rate of 5%.

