Furthermore, the mean 6 month event rate from the meta-analysis of prior treatment studies is 0.38, with both the CHAMPION (0.37) and GUIDE-HF (0.31, NYHA class III) treatment groups with event rates lower than the mean. The lowest 6 month event rate across CardioMEMS control studies of 0.39 occurred in GUIDE-HF (NYHA class III), where modest use of SGLT2i occurred during the trial. We conservatively adjust this lowest observed control event rate down to 0.37 to account for increased SGLT2i utilization.

The table below outlines the data sources used to derive a PG for this endpoint.

Since patient level data was not available and summary data was limited in scope, analysis was based on the numbers of events reported from each study and the number of enrolled subjects was for denominator, assuming all subjects were followed for the corresponding time period. Accordingly, the estimates are likely conservative underestimates of true rates since complete follow-up on all subjects was unlikely.

For studies reporting only 12 month rates, estimates of 6 month rates were estimated via an exponential distribution. For example, for a study with a reported 12 month rate, r_{12} , we calculated the 6 month rate, r_6 , as:

$$r_6 = 1 - \exp(\log_n(1 - r_{12})/2)$$

where the division by two (2) accounts for a calculation of the rate for half the follow-up time (i.e. a linearized rate). When possible, events of each type (HF related hospitalization and death) were

^a Adjustment applied assuming 50% use of SGLT2i at the average hazard ratio observed across EMPEROR Preserved, EMPEROR REDUCED, DAPA-HF for NYHA III subjects.

calculated separately and summed to produce the composite event counts and the corresponding composite rate. Rates are calculated as numbers of events over numbers of subjects.

Active Treatment - updated 6 Month Rates with calculation details

Study/Publication	Number of Subjects ¹	Events	Rate ²	Details
CHAMPION ¹⁹	270	99	0.37	
 - 6 month HFH rate reported as 0.31, yielding approx. 84 events - 15 deaths reported - Adding calculated 6 month HFH events and deaths yields 99 events
MEMS PAS ⁴⁴	1200	493	0.41	
 - 6 month rate calculated via reported 12 month rate of 0.54 - Calculated 6 month HFH rate of 0.32, yielding 386 events - 107 deaths reported - Adding calculated 6 month HFH events and deaths yields 493 events

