MEMS-HF ⁴⁶	234	102	0.44	
 - 6 month HFH calculated via reported 12 month rate of 0.60 - Calculated 6 month HFH rate of 0.37, yielding 86 events - 16 deaths reported - Adding calculated 6 month HFH and deaths yields 102 events
GUIDE-HF ⁵² – NYHA class III only	322	100	0.31	
 - Reported 12 month rate of 0.431/0.089 for HFH/D, for composite of 0.52. - Assuming exponential rate, calculated 6 month rate (events) is 0.31 (100) - Events calculated as 322 subjects x 0.31
Estimate (CI)			0.38 (0.33, 0.44)	

¹ Numbers of subjects are those treated subjects estimated to be followed for 6 month events.

² Estimates for events are based on either reported results or are estimated from published figures. For studies reporting 12 month results, 6 month rates were estimated based on exponential rates.

Altogether, for study success, *the upper confidence bound of the observed event rate* for the planned study must be less than the PG_6 (0.43) and the observed event rate must be less than 0.37. Evaluating the upper bound of the confidence interval for the rate ensures that 1) the observed rate will be comparable to prior studies of active treatment (highest observed value = 0.44), 2) the observed rate will be less than the meta-analytic value derived from prior studies of treatment and control, and 3) the observed rate will be less than the lowest rate observed in the control studies (GUIDE HF). The added requirement for the observed event rate to be less than 0.37 provides further assurance that results are comparable to studies of prior CardioMEMS treatment.

The assumed PROACTIVE-HF population event rate is expected to be 0.34. This assumed event rate is lower than all prior active CardioMEMS treatment rates except for GUIDE-HF. While the

contemporary GUIDE-HF study observed an event rate of 0.31 (NYHA Class III), PROACTIVE-HF has higher NTproBNP thresholds than the GUIDE-HF cohort and we expect subjects with higher NTproBNP levels to more closely align with subjects with a recent hospitalization, which have higher event rates.

The mathematical statement of the null and alternative hypothesis is as follows:

$$H_0: r_6 \geq PG_6$$

$$H_A: r_6 < PG_6$$

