where r_6 is the 6 month rate of primary endpoint events and PG_6 is the performance goal. A value of 0.43 will be used for the goal. The null hypothesis will be rejected if the upper confidence bound for the rate is less than the performance goal, or equivalently, that the corresponding p-value from the hypothesis test is less than 0.025. An observed rate of less than 0.37 and rejection of the null hypothesis indicate that the observed rate is statistically less than the performance goal, indicating clinically acceptable results and study success. Analysis will be based on a Poisson regression approach for the number of events, with the log follow-up time as an offset term. Sensitivity analyses using a negative binomial approach to capture within-subject correlation will be performed.

The study will implant 450 subjects (combined in Cohort #2 and Cohort #3) leading to an expected evaluable cohort of 406 subjects. With a goal of 0.43 and a one-sided 0.025 alpha level, the study will have greater than 80% power assuming a population treatment rate of 0.34. Calculations are based on a one-sample Poisson rate test and were performed with PASS 2021.

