7.1.1. Main analysis

The mathematical statement of the null and alternative hypothesis is as follows:

$$H_0: r_6 \geq PG_6$$

$$H_A: r_6 < PG_6$$

will be used for the goal. The null hypothesis will be rejected if the upper confidence bound for the rate is less than the performance goal, or equivalently, that the corresponding p-value from the hypothesis test is less than 0.025. An observed rate of less than 0.37 and rejection of the null hypothesis indicate that the observed rate is statistically less than the performance goal, indicating clinically acceptable results and study success. Analysis will be based on a Poisson regression approach for the number of events, with the exposure time as an offset term, where r_6 is the 6-month rate of primary endpoint events and PG_6 is the performance goal. A value of 0.43 will be used for the goal.

The test will be based on each subject's total number of events, treatment arm, and exposure time, where a subject's exposure is the time to death, early study discontinuation or 6 months, whichever is smaller.

```
proc genmod data = xxx;  
    model number of events = dummy /*(dummy variable)*/ / noint type3 dist=poisson  
offset=log(exposure_time);  
run;
```

All events until day x, which would be exact 6 months (180 days) post-implant visit would be summarized by cohort. The estimated 6 month incidence of HF related hospitalizations (HFH) or all-cause mortality, along with the 2-sided 95% CIs for the estimated will be presented, and p-value from the hypothesis test. The presentation will also include number of HFH, all-cause mortality, total number of both events, and subjects' event rate of HFH or all-cause mortality is calculated as the total number of observed events per subject divided by the (subject's observed exposure time/180) from implant through 6 months, where a subject's exposure is the time to death, early study discontinuation or 6 months (180 days) post implant visit, whichever is the smallest.

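### At the planned size, the added condition of an observed rate below 0.37 is already implied by the 0.43 upper bound, so it adds no assurance for the primary endpoint

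*Protocol*

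**What the plan says.** Protocol 10.3 tests the six-month rate of heart failure hospitalization or death against a performance goal: "A value of 0.43 will be used for the goal". The upper confidence bound must fall below that goal and, in addition, "the observed event rate must be less than 0.37".

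The second condition is presented as a separate safeguard. Protocol 10.3 and SAP 2.4.1 say that this second "requirement for the observed event rate to be less than 0.37 provides further assurance that results are comparable to studies of prior CardioMEMS treatment". In the synopsis (Sample Size Statistical Rationale) it reads: "The added requirement for the observed rate to be less than 0.37 provides further assurance".

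The figure 0.37 comes from the lowest control rate, 0.39 in the NYHA III part of GUIDE-HF: "We conservatively adjust this lowest observed control event rate down to 0.37 to account for increased SGLT2i utilization". The same section gives 0.38 as the meta-analytic treatment rate and 0.37 as the CHAMPION treatment rate.

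On size, the stated power is "greater than 80% power assuming a population treatment rate of 0.34", computed "With a goal of 0.43 and a one-sided 0.025 alpha level", for 450 implanted and 406 evaluable subjects. The analysis is a Poisson regression with follow-up time as offset. SAP 7.1.1 codes it without a link option, which gives the log link, and says that the estimate "along with the 2-sided 95% CIs for the estimated will be presented".

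**The concern.** An added condition gives added protection only if it can reject a result that the first condition accepts. The gap between 0.37 and 0.43 is about the width of the upper arm of a 95% interval at this sample size, so the two conditions may coincide. If they do, the sentence about comparability with CardioMEMS treatment describes protection that the primary-endpoint rule does not contain. A reader could then take a pass as evidence against the adjusted lowest control rate of 0.37, when the test is only against 0.43. The documents give operating characteristics at a true rate of 0.34 only, so this cannot be seen from the text.

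**Working it through.** **Inputs.** Goal 0.43, added threshold 0.37, one-sided alpha 0.025 (two-sided 95% interval), assumed rate 0.34, 406 evaluable and 450 implanted (Protocol 10.3); cap of 450 implants in Cohorts #2 and #3 (Protocol 6.1); log-link Poisson model with a 180-day unit (SAP 7.1.1). Let T be the total exposure in six-month units and k the total events.

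**1. Reproducing the stated power.** An exact one-sample Poisson test rejects when k ≤ c, where c is the largest count with P(X ≤ c | 0.43T) ≤ 0.025.
- T = 406: null mean 0.43 × 406 = 174.58, c = 148, actual alpha 0.0220. Power at 0.34 (mean 0.34 × 406 = 138.04) is 81.4%.
- T = 450: c = 166, alpha 0.0240, power 86.2%.

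Both agree with the stated figure of more than 80%.

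**2. What each condition accepts.** With the log link the upper limit is U = (k/T) × exp(1.96/√k).

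| T | Largest k with U < 0.43 | Rate | U | U at next count | Largest k with k/T < 0.37 |
|---|---|---|---|---|---|
| 406 | 148 | 0.3645 | 0.428 | 0.431 | 150 |
| 428 (midpoint) | 157 | 0.3668 | 0.429 | 0.431 | 158 |
| 450 | 166 | 0.3689 | 0.4295 | 0.432 | 166 |

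Score and exact Poisson limits give the same maximum counts. Over all exposures from 406 to 450 units, the highest rate that the bound accepts is 0.3693. The 0.37 condition removes no outcome.

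**3. Where it would start to matter.** Set k/T = 0.37 and U = 0.43:
- √k = 1.96 / ln(0.43/0.37) = 1.96 / 0.1503 = 13.04, so k = 170.1
- T = 170.1 / 0.37 = 459.7

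In whole numbers, the condition first rejects an accepted result at 462 units (171 events, rate 0.3701).

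**4. Chance of meeting the full rule,** P(X ≤ c | true rate × T):

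| True rate | T = 406 | T = 450 |
|---|---|---|
| 0.34 | 81.4% | 86.2% |
| 0.37 | 44.9% | 50.5% |
| 0.38 | 32.5% | 37.0% |
| 0.39 | 21.9% | 25.1% |

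These are identical with and without the 0.37 condition. Over every whole number from 406 to 450, the figure at 0.37 runs from 44.6% to 50.9%.

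**5. The 12-month rule, for contrast.** The bound below 0.70 accepts 251 events (0.6182) at 406 and 280 (0.6222) at 450. A rate below 0.59 allows only 239 and 265. There the added condition does restrict.

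**6. Other interval scales (not planned).** A square-root-scale limit accepts 167 events at 450, and an identity-scale limit 168, against 166 allowed by 0.37. The condition would then remove one or two events, and the joint rule would still pass a true rate of 0.37 about 48% to 51% of the time at 406, 428 and 450.

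**The case against.** **The property holds in every passing trial.** Protocol 10.3 frames its aims in observed rates, and on the pooled reading any trial that passes has an observed rate below 0.37, hence also below the 0.38 treatment mean. This stands. What is missing is only an increment beyond the bound. The text partly shows the overlap, because it already credits the upper bound with keeping the observed rate under the lowest control rate.

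**The 0.43 bound also serves the aim.** The goal is the lower of the treatment upper limit and the adjusted control mean, so the bound itself speaks to comparability. A reader might infer that, with the 0.37 condition inert, nothing in the rule addresses comparability. The documents do not support that.

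**A true rate of 0.37 is not clearly a failing device.** It equals the adjusted lowest control rate but also the CHAMPION treatment rate, and lies below the treatment mean. Any point-estimate cutoff at 0.37 passes a true 0.37 about half the time. Reading the 45% to 51% as the chance of approving an ineffective device would be one-sided.

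**No claim of statistical evidence against 0.37 is made.** The protocol says that success is relative to the goal. This is correct and limits the point to the assurance sentence.

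**The redundancy is conditional.** The synopsis treats 450 implants as a floor where Protocol 6.1 treats it as a cap, and Protocol 7.7.2 allows replacement of withdrawn subjects, so an overrun past about 460 units could make the condition bind. SAP 7.1.1 also describes a rate per subject over that subject's own exposure. If the 0.37 check used the mean of those, early deaths would inflate it: in a simulation with assumed rates of 0.29 hospitalizations and 0.05 deaths per six months in 450 subjects (not figures from the documents), the pooled rate averaged 0.34 and the mean per-subject rate 0.58. The pooled reading is the natural one, since the test uses it, but the SAP should say so.

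**Conclusion.** The point holds in conditional form. Under the pooled log-link Poisson analysis, with total exposure up to about 460 six-month units, an upper limit below 0.43 forces an observed rate of at most 0.3645 (406 units) to 0.3689 (450 units). The 0.37 condition rejects nothing further, and the assurance attributed to it in the synopsis, Protocol 10.3 and SAP 2.4.1 is not a property of the primary-endpoint rule. A pass supports, inferentially, a rate below 0.43.

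A reader might infer that the condition can never matter. That goes too far: it would matter with a larger enrollment, a different interval scale or a per-subject rate, and the parallel 12-month condition does matter. Nor is anything miscalculated: the stated power reproduces and the test against 0.43 is unaffected. Extra-Poisson variation hardly moves the pass probability: with assumed variance factors of 1.25 to 2, a true rate of 0.37 passes 46% to 51% of the time. The consequence is an overstated claim, not a wrong pass or fail decision.

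**What to change.** In the protocol synopsis, Protocol 10.3 and SAP 2.4.1:

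- Replace the assurance sentence with a statement that, at 450 subjects or fewer, the 0.37 condition is implied by the 0.43 bound, and that success shows a rate below 0.43.
- Treat comparisons with 0.37 and 0.38 as descriptive: report the observed rate and its 95% interval beside them, and give the pass probabilities at true rates of 0.37 (about 45% to 51%) and 0.39 (about 22% to 25%).
- State that the observed rate in the success rule is the pooled model rate: total events divided by (total exposure/180).
- Reconcile the synopsis floor of 450 implants with the Protocol 6.1 cap of 450.

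The cost is a narrower claim from a pass. Sample size, model and test stay as they are, and the 12-month wording does not need this change.

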10.4 Additional Secondary Efficacy Endpoints

The first secondary efficacy endpoint is incidence of HF Hospitalizations or all-cause mortality at 12 months compared to a PG.

The mean 12 month event rate from the meta-analysis of prior control studies is 0.75, or 0.70 on an adjusted basis to account for SGLT-2i inclusion in the guidelines^b. A 12 month event rate of 0.70 represents a value just below the highest event rate observed across the CardioMEMS treatment studies (0.73 in MEMS-HF) and the upper bound of the overall meta-analytic treatment estimate (0.74). Taking the totality of results from the meta-analysis of active treatment trials, individual

^b Adjustment applied assuming 50% use of SGLT2i at the average hazard ratio observed across EMPEROR Preserved, EMPEROR REDUCED, DAPA-HF for NYHA III subjects.

results of active treatment trials, as well as the meta-analysis of control trials, we set the secondary endpoint performance goal (PG₁₂) at 0.70.

Furthermore, the mean 12 month event rate from the meta-analysis of prior treatment studies is 0.64, with both the CHAMPION (0.6) and GUIDE-HF (0.52, NYHA class III) treatment groups with event rates lower than the mean. The lowest 12 month event rate across CardioMEMS control studies of 0.63 occurred in GUIDE-HF (NYHA class III only), where modest use of SGLT2i occurred during the trial. We conservatively adjust this lowest observed control event rate down to 0.59 to account for increased SGLT2i utilization.

The table below outlines the data sources used to derive a PG for this endpoint.

Active Treatment - updated 12 Month Rates with calculation details

Study/Publication	Number of Subjects ¹	Events	Rate ²	Details
CHAMPION ⁵³	270	162	0.60	- HFH rate of 0.46, yielding approx. 124 events - Mortality rate of 0.14, yielding approx. 38 events - Total events = 124 + 38
MEMS PAS ⁴⁴	1200	840	0.70	- HFH rate of 0.54, yielding 648 events - Mortality rate of 0.16, yielding 192 events - Total events = 648 + 192
MEMS-HF ⁴⁶	234	171	0.73	- HFH rate of 0.60, yielding 140 events - Mortality rate of 0.13, yielding approx. 30 events - Total events = 140 + 31
GUIDE-HF ⁵¹ – NYHA class III only	322	167	0.52	- - HFH rate of 0.431 + plus death rate of 0.0897 - Composite rate = 0.52 - Total events = 322 subjects x 0.52
Estimate CI			0.64 (0.55, 074)	

Altogether, for study success, *the upper confidence bound of the observed event rate* for the planned study must be less than the PG₁₂ (0.70) and the observed event rate must be less than 0.59. Evaluating the upper bound of the confidence interval for the rate ensures that 1) the observed rate will be comparable to prior studies of active treatment (highest observed value = 0.74), 2) the observed rate will be less than the meta-analytic value derived from prior studies of treatment and control, and 3) the observed rate will be less than the lowest rate observed in the

control studies (GUIDE HF). The added requirement for the observed rate to be less than 0.59 provides further assurance that results are comparable to studies of prior treatment.

The assumed PROACTIVE-HF population event rate is expected to be 0.55. This assumed event rate is lower than all prior active CardioMEMS treatment rates except for GUIDE-HF. While the contemporary GUIDE-HF study (NYHA class III only) observed an event rate of 0.52, PROACTIVE-HF has higher NTproBNP thresholds than the GUIDE-HF cohort and we expect subjects with higher NTproBNP levels to more closely align with subjects with a recent hospitalization, which have higher event rates. The mathematical statement of the null and alternative hypothesis for the first secondary efficacy is as follows:

$$H_0: r_{12} \geq PG_{12}$$
$$H_A: r_{12} < PG_{12}$$

where r_{12} is the 12 month rate of secondary endpoint events and PG_{12} is the performance goal. A value of 0.70 will be used for the goal. The null hypothesis will be rejected if the upper confidence bound for the rate is less than the performance goal, or equivalently, that the corresponding p-value from the hypothesis test is less than 0.025. An observed value of less than 0.59 and rejection of the null will indicate that the observed rate is statistically less than the performance goal, indicating clinically acceptable results. Analysis will be based on a Poisson regression approach for the number of events, with the log follow-up time as an offset term. Sensitivity analyses using a negative binomial approach to capture within-subject correlation will be performed.

Sample size calculations for the first secondary endpoint were performed in PASS 2021 and based on an assumed population event rate of 0.55, the sample size of 450 subjects would provide approximately 95% power for the secondary endpoint based on a one-sided 0.025 alpha level. If 406 subjects are followed for 12 months, approximately 95% power will be provided, so that the planned sample size is sufficient in light of potential attrition.

Formal hypothesis testing for the purposes of labeling claims for the first secondary efficacy endpoint will only be performed if the null hypothesis for the primary efficacy endpoint is successfully rejected.

This gatekeeping approach preserves the overall type I error rate. Any other calculated P-values and confidence intervals for secondary endpoints will be nominal, without adjustment for multiple comparisons.

The remaining secondary efficacy endpoints are as follows:

1. Number of HF Hospitalizations at 6 and 12 months post-implant compared to the number of HF Hospitalizations in the 6 and 12 months prior to implant

2. Comparison of the number of HF Hospitalizations or Emergency Department/ Hospital Outpatient IV diuretic visits of Cohort #1 and Cohort #2+#3 at 6 and 12 month post implant
3. Change of NT-pro BNP from Baseline through 6 and 12 months
4. Combined outcome of:
 - a. First and recurrent HF Hospitalizations
 - b. Emergency Department/ Hospital Outpatient IV diuretic visits
 - c. all-cause mortalityat 6 months, added together with equal weighting into a total number of events
5. Heart failure hospitalization or Emergency Department / Hospital Outpatient IV diuretic visits at 6 and 12 months
6. Cardiac and all-cause mortality
7. Days Alive and Out of Hospital (DAOH)
8. IV diuretic visits
9. Heart failure related Medication changes
10. Change in PAP:
 - a. From Baseline through 6 and 12 months in subjects with a baseline mPAP
 - i. above target range
 - ii. within or below target range
 - iii. Overall
 - b. Before and after 6-Minute Walk Test
11. Percentage of device success as documented by ability of the System to successfully transmit PAP data
12. Patient Outcome Measures, measured by KCCQ
13. Functional status improvement, as measured by NYHA and 6-Minute Walk Test
14. Health Economic Analysis

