6.1 Study Flow

The study will implant up to 535 subjects. Assuming a dropout rate of approximately 10% by 6 months, this study will implant a maximum of 450 patients in Cohort #2 and Cohort #3. This is to achieve at least 406 implanted patients with complete follow-up at 6 months. After completion of enrollment and as soon all 406 subjects reach their 6 month follow- up visit, the 6 month primary endpoint data will be used for Premarket Approval (PMA) submission. Up to 85 subjects (cross- over from former **Control Arm**) will continued to be followed in Cohort #1.

[figure not shown]

Figure 9: Study Flow

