Sample size calculations for the first secondary endpoint were performed in PASS 2021 and based on an assumed population event rate of 0.55, the sample size of 450 subjects would provide approximately 95% power for the secondary endpoint based on a one-sided 0.025 alpha level. If 406 subjects are followed for 12 months, approximately 95% power will be provided, so that the planned sample size is sufficient in light of potential attrition.

Formal hypothesis testing for the purposes of labeling claims for the first secondary efficacy endpoint will only be performed if the null hypothesis for the primary efficacy endpoint is successfully rejected.

This gatekeeping approach preserves the overall type I error rate. Any other calculated p-values and confidence intervals for secondary endpoints will be nominal, without adjustment for multiple comparisons.

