7.1.4. Incidence of HF Hospitalizations or all-cause mortality at 12 months

The mathematical statement of the null and alternative hypothesis for the first secondary efficacy is as follows:

$$H_0: r_{12} \geq PG_{12}$$

$$H_A: r_{12} < PG_{12}$$

where r_{12} is the 12 month rate of secondary endpoint events and PG_{12} is the performance goal. A value of 0.70 will be used for the goal. The null hypothesis will be rejected if the upper confidence bound for the rate is less than the performance goal, or equivalently, that the corresponding p-value from the hypothesis test is less than 0.025. An observed value of less than 0.59 and rejection of the null will indicate that the observed rate is statistically less than the performance goal, indicating clinically acceptable results.

Analysis will be based on a Poisson regression approach for the number of events, with the log follow-up time as an offset term. Sensitivity analyses using a negative binomial approach to capture within-subject correlation will be performed.

12 month incidence of HF related hospitalizations (HFH) or all-cause mortality will be analyzed on the mITT, PP and Cohort #1 population in a similar manner to the primary efficacy endpoint.

7.1.5. Number of HF Hospitalizations at 6 and 12 months post-implant compared to the number of HF Hospitalizations in the 6 and 12 months prior to implant

Heart Failure hospitalizations will be summarized by cohort presenting number of subjects without any hospitalizations at 6 and 12 months post-implant visit, number of subjects with any hospitalizations at 6 and 12 months post-implant visit, number of hospitalizations per subject at 6 and 12 months post-implant visit, and mean number of hospitalizations per subjects at 6 and 12 months post-implant visit. Similar presentation will be done based on the CRF information on the number of hospitalizations in the 6 and 12 months prior to implant. 95 % Clopper-Pearson confidence interval (CI) will be provided in addition for the frequencies as applicable. In additional, Wilcoxon rank sum tests will be performed to compare the number of hospitalizations per subject at 12 months post-implant visit with 12 months prior-implant visit, and compare the number of hospitalizations per subject at 6 months post-implant visit with 6 months prior-implant visit.

The 6 and 12 months timepoint is independently of visit information and is calculated as:

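### The stated 95% power at 12 months is for rejecting 0.70 only; under the plan's full success rule, before the primary-endpoint precondition, it is about 86% (406 subjects) or 87% (450)

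*Protocol*

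**What the plan says.** The first secondary efficacy endpoint is the 12-month rate of HF hospitalization or death, tested against a performance goal of 0.70 with an assumed true rate of 0.55. Protocol 10.4 requires the upper confidence bound to be below 0.70 and adds that "the observed event rate must be less than 0.59". SAP 2.4.2 carries the same pair of conditions, and SAP 7.1.4 repeats them in the analysis section: "An observed value of less than 0.59 and rejection of the null will indicate" a clinically acceptable result.

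The power statement names only the alpha level. Protocol 10.4 gives "power for the secondary endpoint based on a one-sided 0.025 alpha level", and SAP 2.4.2 says "the sample size of 450 subjects would provide approximately 95% power for the secondary endpoint". For the reduced sample, Protocol 10.4 adds "If 406 subjects are followed for 12 months, approximately 95% power will be provided". From this it draws the conclusion on enrolment: "so that the planned sample size is sufficient in light of potential attrition". Neither document mentions 0.59 in this statement.

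Formal testing of the endpoint "will only be performed if the null hypothesis for the primary efficacy endpoint is successfully rejected". The step from 450 to 406 subjects comes from Protocol 6.1: "Assuming a dropout rate of approximately 10% by 6 months".

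**The concern.** A reader will take power for the endpoint to mean the chance of meeting the success rule set out just above it. If the second condition is stricter than the test, that chance is lower than the stated figure, and the sentence saying the sample is large enough after attrition rests on a number for a different event. This is the only secondary efficacy endpoint given a formal test for labeling claims, so its chance of success should be stated correctly.

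**Working it through.** **Inputs.** From Protocol 10.4 (same in SAP 2.4.2): goal 0.70, true rate 0.55, observed-rate limit 0.59, one-sided alpha 0.025, Poisson model, n = 450 or 406. Each subject is given one full 12-month unit of follow-up, so the event count X is Poisson with mean n × rate.

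**Step 1: reproduce the stated 95%.** Two normal approximations for the test against 0.70 alone:
- Null variance: Φ((0.70 − 0.55)√(n/0.70) − 1.96) gives 95.1% (406) and 96.7% (450).
- Log rate: Φ(ln(0.70/0.55)√(0.55n) − 1.96) gives 95.0% (406) and 96.7% (450).

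So the stated figure is power to reject 0.70 and nothing more.

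**Step 2: exact power for the test alone.** Find the largest c with P(X ≤ c | 0.70n) ≤ 0.025, then evaluate P(X ≤ c | 0.55n). The log-scale Wald upper bound gives the same c.

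**Step 3: add the 0.59 condition.** The largest count with X/n < 0.59 is 239 for 406 subjects (0.59 × 406 = 239.54) and 265 for 450 (0.59 × 450 = 265.5). Power for the full rule is P(X ≤ the smaller of the two limits | 0.55n).

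| | n = 406 | n = 450 |
|---|---|---|
| Mean under 0.70 | 284.2 | 315 |
| Mean under 0.55 | 223.3 | 247.5 |
| Largest count rejecting 0.70 | 251 (rate 0.618) | 280 (rate 0.622) |
| Power, test alone | 96.9% | 98.0% |
| Largest count with rate below 0.59 | 239 (0.5887) | 265 (0.5889) |
| **Power, both conditions** | **86.0%** | **87.3%** |

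The 0.59 limit binds in both columns. A simple Wald bound would move the test limits to 253 and 282, so 0.59 still binds. As a check, Φ((0.59 − 0.55)/√(0.55/n)) gives 86.1% and 87.4%.

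**Step 4: the precondition on the primary endpoint.** The plan assumes 0.34 events per subject by 6 months and 0.55 by 12 months, leaving 0.55 − 0.34 = 0.21 for the second half-year. Independent Poisson counts in the two halves are an assumption made here; the documents do not state it. The largest 6-month count rejecting 0.43 is 148 (406) or 166 (450).

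| | n = 406 | n = 450 |
|---|---|---|
| Primary null rejected | 81.4% | 86.2% |
| Primary null rejected and both 12-month conditions met | 77.1% | 81.2% |
| Both 12-month conditions met, given primary null rejected | 94.7% | 94.2% |
| Primary null and 0.70 rejected, 0.59 missed | 4.0% | 4.8% |

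A simulation of 2,000,000 trials gave 77.1% and 81.2% for the second row and 4.0% and 4.8% for the last.

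**Step 5: the 6-month endpoint for comparison.** It has the same two-part form (0.43 and 0.37). With the exact or log-scale bound, rejection at 406 subjects needs at most 148 events, a rate of 0.3645, already below 0.37. At 450 subjects both limits are 166. The second condition costs nothing there, so the primary power statement also describes its full rule.

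**Step 6: over-dispersion.** The documents give no figure. At assumed variance-to-mean ratios of 1.25 to 2, full-rule power at 12 months before the precondition falls to about 83% to 78% (406) or 85% to 79% (450).

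**The case against.** The strongest reply is that the 95% is not a mistake. Power conventionally means the probability of rejecting the null, the only 12-month hypotheses written down concern 0.70, and 0.59 is a point-estimate criterion that carries no alpha. For that event the figure is right, if anything slightly low. This stands, and the fix keeps the 95%. But the plan says the observed rate must be below 0.59, calls the figure power for the endpoint, and bases sufficiency on it, so the unlabelled number still misleads.

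A second reply is that 86% is itself incomplete because the formal test is run only after the primary null is rejected. Given that rejection, the two-condition probability is about 94% to 95%, close to the stated figure. This is fair, and it is why 86% has to be labelled as not counting the precondition. It does not rescue the plan's figure: the plan presents no conditional calculation, and the conditional value depends on the independence assumption. The unconditional chance of passing both stages at 406 subjects is 77.1%, which is lower still.

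Third, neither 406 nor 450 full years is the true exposure. The analysis uses all implanted subjects with a follow-up offset, and the dropout assumption is by 6 months, not 12. That also stands. The 406 figure is used because the plan uses it for its attrition case, and the gap between the two is only about one percentage point.

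Finally, no design decision changes. That is true, and it limits the weight of the point.

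**Conclusion.** The concern holds. The stated 95% describes rejection of 0.70 alone. Under the plan's own two-condition rule, power is 86.0% with 406 subjects and 87.3% with 450, which is 9 and about 8 points below the stated figure and about 11 points below the exact power of the test alone. Put the other way, the chance of missing success at 406 subjects is about 14%, not about 5%.

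This rests on a true rate of 0.55, Poisson variance, full 12-month follow-up, and no allowance for the precondition on the primary endpoint. Over-dispersion would lower the figures. At 86% the endpoint is still above the level of just over 80% claimed for the primary endpoint, so the sample size remains defensible; that comparison also leaves the precondition out. This is a correction worth making to a figure the plan relies on, not a reason to change the trial.

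**What to change.** In Protocol 10.4 and SAP 2.4.2:

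1. Label the 95% as power to reject 0.70 in the one-sided 0.025 test alone.
2. Add a sentence such as: *At a true rate of 0.55, assuming Poisson variance and full 12-month follow-up, and not accounting for the requirement that the primary null be rejected first, power to meet both conditions (upper bound below 0.70 and observed rate below 0.59) is about 86% with 406 subjects and 87% with 450.*
3. Rest the sentence on sufficiency after attrition on the 86% figure.

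The 6-month text needs no change. The cost is wording in two places and a less favourable stated figure. Enrolment, thresholds and analysis stay as they are.
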